8. **Passive surveillance of practitioner's adherence to study protocol:** We are making no intrusive efforts to monitor adherence to the study protocol by practice clinicians or staff after initial observations to assess the effectiveness of BP measurement training. Beyond offering opportunities for training, we are not being proscriptive about how the intervention should be delivered. We are offering toolkits and allowing practice teams to drive the content, intensity, and format of the intervention.
9. **Inclusive analysis of primary outcomes:** Our analyses will include all study patients regardless of compliance with the recommended intervention protocol (i.e., intent-to-treat). We are interested in whether the interventions work under usual conditions.
10. **Collaborations:** We partnered with a primary care association, MACHC, and built on their relationships with FQHCs in Maryland to secure health system partners.
11. **Allowing for site flexibility:** We are balancing a need for fidelity in implementation with the practice sites' need to tailor the interventions for their individual locations. For instance, we are providing a set amount of funding for staffing the interventions to each practice along with some suggestions on how to allocate the funds, however we are leaving the exact disposition of the funds up to each system.
12. **Generalizability:** By measuring the fidelity of the intervention implementation while allowing for tailoring to individual practices, we hope to be able to show that our interventions can be successfully implemented in a wide variety of settings.

[figure not shown]
G. Randomization and intervention rollout

1. **Randomization Scheme.** Practice randomization took place early in the UH3 phase after all original 30 practices were identified. Our analysis will be conducted at both practice and patient levels. We combined practice networks as necessary to create two cohorts. All of the original participating practices from a health system are in the same cohort. Randomization was stratified by practice network and blocked to balance the intervention allocation within networks (to the degree possible if an odd number of practices in a network) and cohort. Health systems learned the outcome of the randomization in March 2017. They did not share the outcomes of randomization with the individual practices until after blood pressure measurement training had been completed.

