We put considerable thought into the best way to allocate the new practice since all of the practices had already been randomized and informed of their condition, and trial preparations had already progressed to the point where re-randomizing all sites was not feasible. We decided that we should follow our original randomization procedure, i.e., combining two health systems with odd numbers of practices and constraining the last randomization so that there is equal allocation. We performed the constrained randomization because the number of clusters (practices; $n=30$) is relatively small and we wanted to optimize our power. If we had not constrained the randomization, which was stratified by health system, there could have been a fairly large imbalance in the allocation and that imbalance could become worse if we lose any other practices over the course of the study.

The health system adding practices originally had an even number of practices so there was equal allocation at that health system. Fortunately, at the health system where we lost a practice, there remained an even number of practices and they were equally allocated to intervention arms. We could constrain randomization to have equal allocation. The new practice being assigned to the same intervention arm as the practice that we lost (in this case, the CC/Stepped Care arm).

In summary, given that randomization had already occurred for all of the other practices and implementation had begun, it was not feasible to completely re-randomize. If we had added the new practice to the randomization of the health system to which it belongs, then we would have had two health systems with an odd number of practices and neither in a constrained randomization.

In addition to the closure of a practice in 2017, the same health system experienced a change in leadership in the fall of 2017. In January 2018, the new leadership informed us that they no longer wished to participate in the RICH LIFE Project. We had completed BP training at this health system; however, patient recruitment had not begun at any of the FHCB practices.

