Given the stage of the trial, it was too late to try to recruit a new health system. However, we did not want to drop down to 28 practices and possibly be underpowered to achieve our aims. One of our other health systems offered us the opportunity to select two out of three additional practices in their system that meet eligibility criteria for the trial. Two of these practices were in Baltimore City, which was where the practices we lost were also located. With approval from the DSMB, we enrolled the new practices and randomized them using a blocked randomization (1 in each arm).

E. Practice compensation: Each health system is compensated based on the number of practices participating and the arms to which the practices will be randomized. Below is an example of the compensation scheme for a health system with eight participating practices, four of which are randomized to the CC/Stepped Care arm. Based on our past experiences and to allow us to plan for equity in the amounts we provide to each of the systems that we are partnering with, we are proposing the funds be spent in the following manner. However, it is up to each system’s discretion as to how the funds are actually spent, and they may choose to redistribute the provided funds in a manner that aligns with their organization’s needs, structure, and policies.

[figure not shown]
| Table 4: Sample Health System Compensation Plan | | | |
|--|----------|-----------------|-----------------|
| Salary support | | | |
| Development Year: October 2015 – August 2016 | | | |
| System level champion | \$3000 | 1 site-wide | \$3000 |
| 2 Years of Active Intervention: TBD | | | |
| System level champion | \$3000 | 1 site-wide | \$3000/year |
| System level administrative champion | \$1600 | 1 site-wide | \$2000/year |
| Practice level physician champion | \$1000 | 8 sites | \$8000/year |
| CMA Super User stipend | \$200 | 8 sites | \$1600/year |
| Salary support for Care Manager* | \$16,000 | 4 sites | \$80,000/year |
| Salary & benefits to fully support practice CHW* | \$35,682 | 4 sites | \$142,728 /year |
| 1 Year of Observation without Intervention: TBD | | | |
| System level champion | \$3000 | 1 site-wide | \$3000/year |
| CMA Super User stipend | \$200 | 8 sites | \$1600/year |
| Analysis Year: September 2019 – August 2020 | | | |
| System level champion | \$3000 | 1 site-wide | \$3000 |
| CMA Super User stipend | \$200 | 8 sites | \$1600/year |
| Additional Material Support | | | |

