We will use descriptive statistics to characterize the organizations, providers, and patients, using means and standard deviations, medians and interquartile ranges, or frequencies and percentages where appropriate. Descriptive statistics of central tendency and variability will be generated for outcomes. The distributions of each continuous outcome variable will be assessed for normality, and appropriate transformations will be made if necessary. Two-sample t-tests, Wilcoxon rank-sum tests, and Fisher’s exact test will be used to compare baseline demographic and practice characteristics across intervention arms.

Primary statistical analyses testing the differences in outcome (or change in outcome over time) between intervention groups will be conducted using the intention-to-treat principle. For our clinical outcomes at our primary endpoint of 12 month follow-up, we will select the EMR measure that is closest to 12 months following the baseline survey (enrollment date) for each patient as long as it is within the 6 month window.

General Approach

These analyses will utilize all available data through modeling approaches for correlated outcomes. All missing data will be assumed to be missing at random (MAR) conditioning on the observed data, and models will be adjusted for characteristics associated with missingness and key variables not balanced by the cluster randomization. In sensitivity analyses, missing data will be imputed using likelihood based longitudinal models developed under the MAR assumption. Missing data under plausible informative missing scenarios will be multiple-imputed using these likelihood based models with the mean models tuned according to the plausible informative missing scenarios. These sensitivity analyses will verify the robustness of the results derived under MAR assumption. All tests will be two-sided and significance will be set at $\alpha < 0.05$. Analyses will be conducted using SAS version 9.4 or higher (SAS Institute, Inc., Cary, NC) or Stata SE14 or higher (StataCorp, College Station, TX).

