We will use mixed-effects regression models for continuous outcomes and Generalized Estimating Equations (GEE) analysis for dichotomous outcomes. For mixed-effects regression modeling, we will assume an unstructured correlation structure for longitudinal analyses of outcomes with repeated measurements over time, employ random effects to address clustering by practices, include appropriate covariate adjustment in the fixed effects, and use robust estimates for statistical inferences. The GEE approach is robust to outcome correlation misspecification, so we will just assume an exchangeable correlation structure for the outcomes, include appropriate covariates in the mean model, and use robust estimates for statistical inferences. We will use mixed-effects regression models under the MAR assumption as the basis to conduct multiple imputation for missing BP data or other outcomes as appropriate. In sensitivity analyses evaluating potential impacts under sensible informative missing

(NMAR) scenarios, we will preserve the mixed-effects regression based variance-covariance estimates, and manipulate the mean model under each informative missing scenario to carry out multiple imputation. Missing binary outcomes (e.g., controlled BP or lipids) will be derived based on multiple-imputed continuous values using appropriate observed data likelihood models as described.

Statistical analysis plan for primary outcomes

For the primary clinical outcome of BP control at 12 months we will model the binary variable BP controlled (yes/no) at 12 months using GEE with a logit link on the intervention arm indicator (CC/Stepped Care arm vs. SCP arm). Additional covariates will be included as appropriate as described previously, including appropriate cluster level characteristics and variables associated with occurrence of missing data. With correctly specified mean model, the GEE is robust to misspecification of correlation structure so the statistical inferences will account for outcome correlation due to patients clustering within practice and be valid under MCAR. The regression coefficient for the intervention arm indicator estimates the log-odds ratio of BP control at 12 months for the CC/Stepped Care arm to the SCP arm. Multiple imputation of missing BP outcomes will be carried out to impute the missing BP control outcomes to produce proper inferences under MAR and to conduct sensitive analyses under NMAR scenarios.

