For the primary patient-reported outcome of change from baseline in PAM-13 score at 12 months, we will model the baseline and 12-month PAM-13 measurements using a mixed-effects linear regression model, with the intervention arm indicator (CC/Stepped Care arm vs. SCP arm), 12-month time indicator, and the cross-product term of intervention by time interaction as the fixed mean effects, the practice indicator as a random effect, and additional covariates included as fixed effects as appropriate as described previously. The fixed effect regression coefficient for the cross-product term of intervention by time estimates the mean difference of 12 month change in PAM-13 between arms.

Statistical Analysis Plan for Secondary Outcomes

For the outcomes of systolic and diastolic BP measures at 12 months, we will select the blood pressure measure that is closest to 12 months of follow-up for each patient as long as it is within the 6-month window (either direction). We will model the baseline and 12-month BP measurements using a mixed-effects linear regression model, with the intervention arm indicator (CC/Stepped Care arm vs. SCP arm), 12-month time indicator, and the cross-product term of intervention by time interaction as the fixed mean effects, the practice indicator as a random effect, and adjusting for additional covariates as fixed effects as described previously. The random effect for the cluster ID will be used to capture the outcome correlation for patients nested within the cluster. The fixed effect regression coefficient for the cross-product term of intervention by time estimates the mean difference of 12 month change in BPs between arms.

For the other secondary measures, e.g., laboratory measures of hemoglobin A1c and lipids, we will use methods similar to the assessment of 12 month outcomes for blood pressure, i.e., select the within window measure in the EMR closest to 12 months after baseline and use mixed-effects linear regression or GEE models to assess the outcomes while controlling for outcome clustering within practice.

Subgroup and Exploratory Analyses

Durability of intervention effect at 24 months

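### Randomisation was stratified by practice network, but no analysis model commits to network; naming it is worth doing only together with a small-sample variance correction

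*Combined protocol and SAP*

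**What the plan says.** Section 3G (Randomization Scheme) sets the design: "Randomization was stratified by practice network and blocked to balance the intervention allocation within networks", and by cohort. All original practices of a system share one cohort, so for them network determines cohort. Section 4D confirms stratification by health system and describes how odd counts were handled: "combining two health systems with odd numbers of practices and constraining the last randomization so that there is equal allocation". It also describes a practice added in 2017, which took the arm of the practice it replaced, and a later pair from one participating system, randomised one to each arm.

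In Section 8 the BP-control GEE names one term, the arm indicator. For the rest: "Additional covariates will be included as appropriate as described previously, including appropriate cluster level characteristics and variables associated with occurrence of missing data". That refers back to the General Approach, under which "models will be adjusted for characteristics associated with missingness and key variables not balanced by the cluster randomization". For GEE, the analysis will "include appropriate covariates in the mean model, and use robust estimates for statistical inferences"; the plan gives neither a small-sample correction nor a reference distribution. The PAM-13, systolic BP and diastolic BP models contain arm, time, arm by time, a practice random effect and covariates as appropriate. In the PAM-13 model the "cross-product term of intervention by time estimates the mean difference of 12 month change in PAM-13 between arms", and the BP models are built in the same way. None of these models names network or health system. Section 11B mentions a practice-network variable, so the variable appears to be available.

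**The concern.** An analysis should normally reflect the groups within which the trial randomised. Balancing arms within networks removes most between-network variation from the arm contrast. An analysis that ignores network leaves that variation in its standard error. If networks differ in BP control, the standard error is then too large, the test too strict, and some of the power bought by stratifying is lost.

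The choice is also open. An analyst could leave network out or bring it in as a cluster-level characteristic, and both fit the text. With 30 practices the two routes have different error rates unless the variance estimate is corrected for the small number of clusters. On a primary outcome that should be settled in advance. The open covariate rule adds some further discretion.

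**Working it through.** **1. The plan's own figure.** Inputs from Section 8, Power calculation: ICC 0.05, 15 practices of 50 per arm, two-sided alpha 0.05, 80% power. Design effect 1 + 49 x 0.05 = 3.45; effective n = 750/3.45 = 217.4 per arm. A noncentral t with 30 - 2 = 28 df gives 0.2784. The stated 0.278 reproduces.

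**2. Layout (rebuilt from Sections 4C and 4D).** The non-FQHC system has 11 practices. The Reading FQHC has 2 (the count goes from 19 to 21). The Eastern Shore system has 6: the text says five sites, but the count goes from 21 to 27. Two FQHC systems share 19 - 10 = 9, with a 5/4 split assumed. The one-to-one pair belongs to an unnamed participating system. Total: 11 + 2 + 6 + 9 + 2 = 30 practices in five systems. Main case: 13/6/5/4/2, with CC/Stepped Care practices 7/3/2/2/1.

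**3. Direction of the effect.** Let s be the share of between-practice variance that lies between networks (assumed; not in the documents). A practice mean has variance 0.05 + 0.95/50 = 0.069. With arms balanced within network, the arm contrast carries only about 0.05(1 - s) + 0.019, while an analysis without network estimates about 0.069.
- s = 30%: 0.054/0.069 = 0.78, so the true standard error is about 88% of the estimated one.
- s = 50%: 0.044/0.069 = 0.64, or about 80%.

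**4. Size, by simulation of the BP-control GEE.** 30 practices of 50, ICC 0.05, logit-normal practice effects, arms permuted within system. Power is for 60% versus 72% controlled (assumed). Ranges cover separate runs of 6,000 to 10,000 trials per setting.

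Corrected test (Kauermann-Carroll sandwich; t on 28 df without network, 24 df with):

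| s | Error, no network | Error, with network | Power change from adding network |
|---|---|---|---|
| 0 | 4.5-4.9% | 4.6-5.2% | -1 point |
| 10% | 4.3-4.6% | 4.8-5.2% | +1 |
| 30% | 3.1-3.4% | 4.6-5.1% | +5 |
| 50% | 2.2-2.6% | 4.9-5.5% | +8 to +9 |

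Absolute power differed by about 2-4 points between runs; the changes agreed. Practice sizes of 20-80 (assumed) gave changes of -1, +1, +6 and +10. Placing the pair in another system moved error by at most about 0.8 points and power by at most about 2.

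Uncorrected sandwich with a z test (one reading of the plan's robust estimates):

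| s | Error, no network | Error, with network |
|---|---|---|
| 0 | 6.6-6.8% | 8.8-9.4% |
| 10% | 6.0-6.4% | 9.0-9.2% |
| 30% | 4.3-5.0% | 8.7-9.4% |
| 50% | 3.4-3.8% | 8.9-9.2% |

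Power of the uncorrected test without network against the corrected test with network, in one set of runs: 77.0 vs 71.2, 79.4 vs 75.4, 80.4 vs 80.5 and 83.4 vs 88.5%. The gain at 50% was about 3-5 points across runs.

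**5. Change models.** A network effect that is constant over time cancels from the arm-by-time term, so network has to enter by time. In 20,000 simulated trials of a linear change model this gave 9.0-9.4% error uncorrected and 5.0-5.1% corrected.

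**6. Cost if s = 0.** Degrees of freedom fall from 28 to 24, and the detectable effect rises from 0.278 to 0.280. With the uneven splits, the effective number of practices per arm is 7 x 6/13 + 3 x 3/6 + 2 x 3/5 + 2 x 2/4 + 1 x 1/2 = 7.43 on the scale where 15 x 15/30 = 7.50. That gives 0.281.

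**7. Open covariate rule.** Ten patient characteristics with ICC 0.05 (assumed), 3,000 null trials per setting, corrected test, and five readings of the rule: no adjustment; imbalance at p<0.05; at p<0.10; standardised difference above 0.1; practice-level p<0.05. Each reading alone keeps 4-5% error. Choosing the most favourable gives 5.5-6.1%, or 6.5-7.4% if network may also be in or out. The odds ratio moves by a median of 1-5% between readings.

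**The case against.** The strongest reply is that stratified allocation already protects the comparison, so omitting network is at worst conservative, and the plan's wording lets network in. That stands as far as it goes: there is no bias, and if networks barely differ the adjustment gains nothing.

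The plan also never states an uncorrected z test, so the 6.7% and 9% figures depend on an assumed implementation. If that implementation is the comparator, the change is not a general power gain: power is lower by about 4-6 points at shares of 0-10%, level at 30% and higher only at 50%. Both points stand. The extra power at low shares does, however, come with an error rate above 5%.

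The handling of the combined odd-numbered systems looks largely moot. The practice counts imply that one of them was the three-practice Baltimore system, which left before recruiting any patient (Section 4D). The replacement practices belong to participating systems, so their network is known.

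A reader might infer that the planned baseline tests would drive covariate choice. With 63 patients per practice, tests that ignore clustering would flag 29/33/60% of patient characteristics at ICCs of 0.04/0.05/0.21 by chance. The documents do not support that inference. Those tests "will be used to compare baseline demographic and practice characteristics across intervention arms", and nothing links them to model selection. The rates are also an upper range that assumes no clustering between networks; at a 50% network share they fall to about 20/22/48%. Baseline imbalance can be known before 12 months; only the predictors of missingness cannot.

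**Conclusion.** The point holds as a gap in the specification of a stratified cluster trial. The trial randomised by network, the plan does not commit to analysing by it, and the correction needed to do so safely on 30 practices is not stated. Three stronger inferences fail: that omission biases the arm effect, that omission in itself inflates type I error, and that naming network is a sufficient fix. Naming it with an uncorrected robust z test would take the error to about 9%.

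With a corrected test, leaving network out costs about 5 power points at a 30% share and 8-9 at 50%, and nothing that matters at 0-10%. Against an uncorrected analysis without network, whose error runs from about 6.7% down to 3.4% as the share rises, the main benefit is an error rate near 5% whatever the share. The sizes rest on assumed network shares, a partly assumed practice layout and 60% versus 72% control. The open covariate list is a secondary and modest issue. The stated detectable effect of 0.278 is correct.

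**What to change.** In the BP-control GEE, enter health system (network) as fixed effects, with each replacement practice assigned to the system it belongs to. In the same sentence, specify a small-sample-corrected sandwich variance (for example Kauermann-Carroll) and a t reference on practices minus practice-level parameters: 30 - 2 - 4 = 24 df with five systems. Do not add network without that correction. In the PAM-13, systolic BP and diastolic BP change models, enter network by time with the same correction.

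Secondarily, replace adjustment for unbalanced key variables with a covariate list fixed before 12-month outcomes are examined, and keep predictors of missingness in the imputation model that the plan already provides for.

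This needs SAP wording and a variance option, and no new data. It uses four degrees of freedom, about one power point if network is not prognostic. The correction itself lowers nominal power at a share of 0 from about 77% to 72%, but the 77% comes with an error rate of about 6.6%. The odds ratio becomes conditional on network: for 60% versus 72% it is (0.72/0.28)/(0.60/0.40) = 1.71 unadjusted, and 1.72, 1.73 and 1.74 at assumed shares of 10, 30 and 50%.
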